5.3 Inclusion Criteria

Inclusion Criteria

- 18 years old or older
- be enrolled in or pending approval for an insurance plan that supports prescription coverage for smoking cessation medication (including Medicare part D, Medicaid, private insurance, Federal or other governmental, or other insurance) or willing and able to purchase smoking cessation medication and pay for healthcare out of pocket to facilitate delivery of medications
- have a regular provider/PCP or have access to a free or low cost clinic for regular clinical care that can prescribe smoking cessation medication; if patient does not have a PCP, the study team may collaborate with the patient to establish a primary care provider
- agree to quit or try to quit smoking upon study enrollment
- be a daily smoker when smoking normally during the month prior to entering the study
- be medically eligible to use varenicline*
- be medically eligible to use nicotine replacement therapy **
- have received medication recommendations from a tobacco counselor
- agree to take smoking cessation medication (i.e., varenicline OR nicotine replacement therapy) home and consider using it
- have a cell phone or landline that can be reached directly (i.e., without transfer)
- have a permanent address where they live and can receive mail
- estimated life expectancy of at least one year or greater

*Medical eligibility to take varenicline is defined by absence of the following:

- Serious brain condition that impairs cognition (including but not limited to dementia, delirium, brain tumors/metastases, uncontrolled seizures (i.e., seizures within the past 3 mo.))
- pregnancy/planning to become pregnant/breastfeeding in the next year
- history of allergic reaction to varenicline
- unstable/uncontrolled mental health condition:
 - a. altered mental status (e.g., delirium, hallucinations) **OR**
 - b. serious psychiatric symptoms in the past 6 months as defined by suicidal ideation or attempt, hospitalization or ED visit involving a psychiatric condition (e.g., depression, anxiety, bipolar, schizophrenia, schizoaffective disorder, PTSD, substance use (e.g., overdose, other related) **OR**
 - c. changes in psychiatric medication within the past 3 months
- if alcohol use; history of blackouts or seizures with drinking

** Medical eligibility to use nicotine replacement therapy is defined by absence of the following:

- o unstable from cardiovascular perspective
- current or history of Buerger's disease (also called thromboangiitis obliterans)
- pregnant/planning to become pregnant/breastfeeding in the next year

5.4 Exclusion Criteria

Exclusion Criteria

- insufficient time to perform and complete the enrollment process
- barrier to effective communication (including low English proficiency)
- not cognitively able to participate in the study
- too ill, on hospice, or physically unable to participate in the follow-up process
- previously completed the MIST study or is currently enrolled in a quit smoking study that involves a medication-based treatment
- estimated life expectancy of less than one year

5.5 Informed Consent

Informed consent for NMR Screening: Potentially eligible smokers who are counseled in the hospital or by phone by a CTTS will be told briefly about the study and, if interested, the CTTS will obtain a signed screening consent from the patient for NMR sample. An RA may also obtain screening consent for NMR.

Informed consent for full study enrollment: Study staff will perform informed consent. Potential participants will be told that their participation is completely voluntary, and that they can opt out at any time or refuse to participate in any portion of the study. During the consent process, potential participants will be informed of all study procedures, including possible side effects of medications used. The informed consent document will state that the study is being done as a collaboration between VUMC and TelASK. Potential participants will be informed that in order to make the phone calls, TelASK will be given information such as their name, study ID, phone number, sex, preference for time of call, and the date that they are discharged from the hospital or enrolled in the study. There is a small but potential risk of data breach with this transfer of information. However, TelASK-generated IVR calls are becoming an integral part of the clinical care of smoking in multiple healthcare systems across North America. The consent will indicate that participants may be invited to participate in future studies.

Whenever possible, the consent process will be conducted electronically using REDCap, a secure, web-based, HIPAA-compliant, data collection platform. REDCap has a user management system that allows project owners to grant and control varying levels of access to other users (e.g., viewing of data collection instruments and data may be specified as read only). Patient signatures can be obtained as typed or written signature via stylus/cursor. After consenting, patients will be provided with a printed or e-mailed pdf copy of the consent document or a web link to the consent. The web link provides access to a ROCKET site containing their signed consent form. Signed consent documents will NOT be housed electronically on ROCKET.

5.6 Baseline Survey and EHR Data (see Table 1, baseline column)

Baseline data are collected from the medical chart, Counselor Screening Form, RA Screening Form, as well as the Baseline Survey. Data collection will include items such as: Sociodemographic factors (age, sex, education, race/ethnicity, employment, living situation, health insurance type), admitting diagnosis category (cardiac/noncardiac), tobacco use history (years of smoking; use of other tobacco products; Heaviness of Smoking Index, [38] measures of nicotine dependence (cigarettes smoked/day in month before admission and time to first morning cigarette)), rules for smoking in home, [39]alcohol use (AUDIT-C a 3-item survey assessing frequency and quantity of alcohol consumption that predicts problem drinking), [40] depressed mood and anxiety (PHQ-4, a validated screening test for depression and anxiety),[41] intention to remain abstinent from tobacco after study enrollment, pre-existing medical conditions, past use of FDA-approved smoking cessation medications, confidence to quit [42, 43], social support for quitting, perceived health risks of smoking and benefits of quitting,[44] optimism/pessimism as captured by the Life Orientation Test,[45] delay discounting Task (5 Trial Delay Discounting, Tangney et al. Brief Self-Control Scale), [46-48] and detailed contact information for the patient and an alternative contact.

Some of these data are routinely collected by the CTTS and entered into the EHR and/or TTS electronic database; other data are collected by the study RA using a password protected iPad or computer connected to the hospital's secure wireless connection. Study RAs will administer the baseline questionnaire via REDCap[49] (or paper, if needed). All baseline data are entered securely into REDCap. If needed during a power loss, paper forms will be used during enrollment and stored securely in a locked cabinet that only study staff will have the ability to access.

5.7 Baseline blood sample collection

During screening/enrollment, we will attempt to collect a blood sample of approximately 15 ml (3 teaspoons) at the bedside or at an outpatient lab such as VUMC OHO or Cool Springs by clinical phlebotomy/study staff. Blood samples will be used for determination of nicotine and metabolites (for NMR) and future analysis of genetics and other potentially relevant biological markers. Participants will be asked to consent for these data to be collected for the proposed research project and for potential future research. Participants will be advised that blood may be discarded under certain circumstances (e.g., if they elect to not enroll in the study or are deemed ineligible after the NMR blood draw).

Blood sample for NMR test: Often temporarily stored blood is available through the Clinical Pathology Laboratory that can be used for NMR testing. When no stored blood is available, or if time constraints preclude locating and pulling stored blood, a fresh blood sample will be collected for NMR testing. Stored blood may be used when a patient's health precludes a fresh blood draw, not limited to anemia (where hemoglobin lab results are less than 8), hemophilia, and other appropriate disorders or states.

Blood sample for future potential genetic and other analyses:

The NIH's precision medicine initiative, All of Us, aims to understand how genetics, in conjunction with a person's environment and lifestyle, can optimize prevention and treatment of illness. The GSCAN results recently published in Nature Genetics [50] identified hundreds of new genetic variants related to smoking initiation, rate, maintenance, cessation, and substance use. New information continues to become available regarding the role of genetic variation in smoking cessation and response to pharmacotherapy and substance use more broadly. In instances where stored blood is used and supply is limited, NMR test will be prioritized. If a sufficient blood sample cannot be obtained for future genetics research, study staff will collect saliva instead.

5.8 Randomization

Patients can be randomized into the study once the NMR test has resulted. Randomization will be stratified on three factors: (1) primary admitting diagnosis (cardiac vs. other); (2) cigarettes/day (≥10, <10); (3) primary insurance (Medicaid, Medicare with Part D, Private Insurance, Federal/Other Governmental/Other Insurance); and (4) NMR status ("normal"/"slow") to ensure that the treatment groups are balanced. After the patient enrolls, the RA will be directed to the electronic randomization screen in REDCap, which, once submitted, automatically assigns the participant to a randomization group.

Blinding: The nature of the study precludes blinding of patients or research staff to the study condition.

Participants will receive a handout describing their assigned treatment. For those randomized to the MIST (precision) arm, the handout will include information on the NMR result and recommended medication. In the event that a participant is enrolled before a valid NMR result is received, study staff may contact the participant via phone/text/email (per participant preference) to notify of randomization status and initiate post-randomization procedures including facilitation of smoking cessation medication. Those randomized to the Usual Care arm will receive their NMR result at study completion, 12 months post-study enrollment; participants in the Usual Care arm who withdraw from the study will not be provided precision care information.

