5.9 Outcome Assessments – Surveys (Table 1) and Biochemical Samples (Table 2)

Follow up surveys: (Table 1) See Page 32 for full table. A brief follow up survey will be sent to participants through a REDCap-enabled Twilio survey link via email/text message based upon participants preference as stated at enrollment. The surveys will be sent to participants at approximately 1, 3, 6, and 12 months after study enrollment. For completeness, smoking status and medication usage outcomes will be assessed at all follow-up time points. Participants who do not respond to survey invites sent through email or text will be contacted by phone and mail. If the participant cannot complete the follow up survey remotely, we will make all efforts to coordinate with the patient during any pending appointments at VUMC so they can complete their survey on a day when they are already scheduled to be at VUMC (e.g. study RA will travel to the One Hundred Oaks clinic of other VUMC clinics to meet participant) If these modes are insufficient to complete surveys, alternative contacts (participant's proxy) will be contacted. When needed, , study staff call participants to administer the survey, making approximately 24 attempts over 4 to 8 weeks. If unsuccessful, participants may be mailed an abbreviated survey containing only the primary and secondary outcome measures. We have successfully administered similar questionnaires for prior studies of hospitalized smokers and low-income smokers residing in the Mid-South. Mid-Atlantic, and New

England regions. Study staff also offer to meet participants at their clinic visits for convenience. Study staff may also extract information from the EHR fields such as smoking status and cigarettes per day, use of other tobacco products, and smoking cessation medication use.

Biochemical Samples

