Aim 1: Biochemical Verification of Self-Reported Abstinence (Table 2, Row 1) For participants who self-report abstinence at the 6 month and/or 12 month follow up surveys, study staff will attempt to biochemically-verify the self-report. Based on prior experience with challenges in obtaining biochemical verification, there will be several options including: (1) saliva cotinine (in- person or mailed); (2) end-expired carbon monoxide (in-person or remote) if participants are unwilling or unable to verify with cotinine (e.g., actively using NRT). Standard saliva cotinine kits will be analyzed by Salimetrics Laboratory or other comparable lab. Smoking abstinence can also be confirmed through in-person or remote carbon monoxide (CO) testing (if a participant is on NRT). If a participant is unable to complete an in-person CO, then a personal CO device (such as a CoVita iCO Smokerlyzer) may be mailed to the participant to complete the CO reading remotely. We have successfully used this protocol for mailed cotinine samples and CO testing in the past. Smoking abstinence will be defined conservatively according to recommended standards. The following cessation milestones will be assessed in addition to point prevalence abstinence (PPA):

- i. *Initial abstinence* is defined as the first instance in which the participant refrains from smoking for at least 24 hours; duration of initial abstinence will also be assessed.
- ii. *Initial lapse,* defined as the first episode of ANY smoking, even a puff, after achieving initial abstinence, will also be assessed.
- iii. Continuous abstinence is defined as no smoking, even a puff, since study enrollment (i.e., achieved PPA at 1, 3, 6, and 12 mo +no smoking in between surveys + biochemical validation of selfreported (SR) PPA at 6, 12 mo). Participants who are unable to biochemically verify abstinence will be assumed to be smoking, by convention, but sensitivity analyses will consider a range of possible odds ratios (1, 2, and 5) linking loss to follow-up and smoking. [51]

| Table 2: Main Ou | itcome Measures by Study | y Aim | | | | |
|-----------------------------------|--|--------------|---|--|--|--|
| Outcome | Measure | Data sources | | | | |
| | | Survey | Other source | | | |
| AIM 1: | SR at 1, 3, 6, 12 m | | | | | |
| Abstinence | Biochem. validation at 6 m (primary study | Х | 12 m* via saliva cotinine <10 ng/ml or expired CO <10ppm | | | |
| AIM 2. | SR at 1 3 6 12 m | | | | | |

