9.0 Statistical Considerations

9.1 Aim 1

The primary study outcome is biochemically-verified self-reported 7-day point prevalence abstinence at 6 months as defined by salivary cotinine level < 10 ng/ml or expired CO <10 ppm. A secondary outcome is biochemically-verified self-reported 7-day point prevalence abstinence at 12 months. Brief surveys will be conducted at 6 and 12 months after study enrollment to determine self-reported abstinence. Biochemical validation of smoking status is accomplished via mailed salivary cotinine samples or expired CO.

Analysis:

The effect of MIST vs. UC on biochemically-verified abstinence at 6 months will be estimated via a relative risk of abstinence and tested at a 5% significance level via a chi-squared test with Yates' continuity correction. The same method will be applied

to the secondary outcome at 12 months. Anticipated loss to follow up is accounted for in the expected approximate UC abstinence rates where persons lost to follow up will be treated as non-abstinent. However, sensitivity analyses will consider a range of possible odds ratios (1, 2, and 5) linking loss to follow-up and smoking. [51] Exploratory analyses testing for effect heterogeneity will use multivariate logistic regression models adjusting for the main effect of a potential modifier and testing for an interaction with the effect of MIST. The potential effect modifiers to be explored are age, race, sex, NMR, and pre-intervention plan to quit.

Power:

Conservatively assuming a biochemically validated abstinence rate of 10% under UC, a chi-squared test on 1000 patients (at 6 months) will detect a MIST abstinence rate of 16.2% (Risk Difference=6.2%, Relative Risk=1.62, Odds Ratio=1.74) with 80% power. Assuming a 15% biochemically validated abstinence rate under UC (at 12 months), a 22.2% rate under MIST (RD=7.2%, RR=1.48, OR=1.62) is detectable with 80% power. Power was estimated via simulating 20K datasets under the settings above in the statistical program R and were checked against the simplified estimates of the pwr package.

9.2 Aim 2

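### Section 5.8 rules out blinding for all research staff, though staff doing the 6- and 12-month follow-up need not know the arm and their effort can affect who counts as abstinent

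*Combined protocol and SAP*

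**What the plan says.** Section 5.8 (Randomization) disposes of blinding in one sentence: "The nature of the study precludes blinding of patients or research staff to the study condition". It makes no exception for follow-up or outcome assessment.

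Section 5.9 gives the follow-up work to study staff. After an automated survey link, and when needed, "study staff call participants to administer the survey, making approximately 24 attempts over 4 to 8 weeks". If that fails, a shortened survey may be posted. For participants who report abstinence at 6 or 12 months, "study staff will attempt to biochemically-verify the self-report", by saliva cotinine or CO; a personal CO device may be posted to those who cannot attend. Section 5.11 has the study RA travel to clinics for the CO test. No separate or masked follow-up team is described.

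On scoring, section 5.9 says: "Participants who are unable to biochemically verify abstinence will be assumed to be smoking, by convention". Section 9.1 says that "persons lost to follow up will be treated as non-abstinent" and adds that "sensitivity analyses will consider a range of possible odds ratios (1, 2, and 5) linking loss to follow-up and smoking". The primary comparison is "tested at a 5% significance level via a chi-squared test with Yates' continuity correction".

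**The concern.** Whoever hands over the NMR result and the recommended medication has to know the arm. A 6-month caller or a CO reader does not: the survey schedule, questionnaire, cut-offs and payments are common to both arms. The pilot in section 3.0 had varenicline prescribing of about 60% in each arm, so hearing which drug a participant takes would not by itself reveal the arm.

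The scoring rule makes this more than a formality. To count as abstinent, a participant must be reached, report abstinence and complete a test. Failure at any step is scored as smoking. One more call, or a CO device posted to one person and not to another, can turn a true quitter from a failure into a success. If staff know the arm and effort drifts with it, the drift passes into the 6-month relative risk. Biochemical verification guards against false claims of abstinence. It does not guard against unequal effort in obtaining the verification.

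**Working it through.** **Inputs from the plan (section 9.1).** N = 1000; 10% verified abstinence under UC at 6 months; 16.2% under MIST; 80% power; two-sided 5% Yates-corrected chi-squared test.

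**Assumptions.** 1:1 allocation, so 500 per arm (the ratio is not stated). No verification rate by arm is given, so all gaps below are assumed.

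**Step 1: reproduce the plan's figure.** Exact binomial enumeration of the Yates test at 10% vs 16.2%, 500 per arm, gives 80.8% power. The stated 80% is confirmed.

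**Step 2: size with equal follow-up.** Under no effect the same test rejects in 3.8% of trials at 10% vs 10%, and in 4.0% at 12% vs 12%. The second figure is the like-for-like benchmark for step 3.

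**Step 3: a verification gap under no true effect.** Observed abstinence = self-reported abstinence × proportion verified. Take 20% self-reported in both arms and 60% verified in UC, so UC is 0.20 × 0.60 = 12%.

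| Verified, UC vs MIST | Observed, UC vs MIST | RR | Rejection rate |
|---|---|---|---|
| 60% vs 60% | 12% vs 12% | 1.00 | 4.0% |
| 60% vs 65% | 12% vs 13% | 1.08 | 6.3% |
| 60% vs 70% | 12% vs 14% | 1.17 | 13.4% |
| 60% vs 75% | 12% vs 15% | 1.25 | 25.4% |

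**Step 4: the same question anchored on the plan's 10% UC rate.** Let capture be the proportion of true quitters who are both reached and verified. Then MIST observed = 10% × (MIST capture ÷ UC capture). The 80% level is the pilot's 6-month reach (section 3.0); 60% and 50% are assumed, since verification adds further loss.

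| UC capture | MIST +5 points: RR, rejection | MIST +10 points: RR, rejection |
|---|---|---|
| 80% | 1.06, 4.9% | 1.13, 8.0% |
| 60% | 1.08, 5.7% | 1.17, 11.4% |
| 50% | 1.10, 6.5% | 1.20, 14.7% |

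The benchmark here is 3.8%. A 5-point gap does little. A 10-point gap raises the false-positive rate to roughly two to four times the benchmark (8.0 ÷ 3.8 = 2.1; 14.7 ÷ 3.8 = 3.9).

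**The case against.** The plan has more protection than the blinding sentence suggests.

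- **A common pathway exists.** Section 5.9 runs from automated link to phone and mail, clinic contact and proxy, and nothing makes it differ by arm. Meeting participants at clinic appointments is not left to choice: sections 4.0, 5.9 and 5.11 commit staff to every effort. Payment for verification is the same in both arms, and saliva goes to an outside laboratory. The remaining discretion lies in the approximate number of calls and in the shortened survey and CO device, which staff may or may not post. This objection stands and narrows the point.
- **Sensitivity analyses are planned.** The odds-ratio analyses (1, 2 and 5) may partly offset unequal reach, if applied within arm. They do not prevent it and leave the primary result unchanged. They are framed around loss to follow-up, and it is not clear that they cover someone who was reached but not verified.
- **A gap could be detected.** A reader might infer that no later analysis could separate unequal chasing from a treatment effect. The documents do not support that. Self-report is collected before verification, so comparing self-reported with verified abstinence by arm would expose a verification gap such as the one in step 3. Missing data are also reviewed monthly (section 10.3), and the DSMB monitors follow-up (section 7.5). These measures detect the problem; they do not prevent it.
- **Masking staff is not a complete remedy.** A reader might also infer that it would remove the bias. Participants know their arm, only MIST participants receive their NMR result at the start, and they may respond or attend for testing differently whatever staff do. Participants may also disclose their arm, and staff contact PCPs, of whom only those in MIST hold NMR results. How often masking would fail cannot be judged from the documents.

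**Conclusion.** The point holds as an avoidable exposure in the design. The statement in 5.8 is broader than the study requires, and it leaves the primary endpoint open to arm-aware differences in follow-up effort. That follow-up staff will know the arm is inferred from this blanket statement; the plan does not say so of them by name.

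The documents do not show that bias will occur. Under the assumptions in step 3, false-positive rates are 6.3% to 25.4% for gaps of 5 to 15 points, against 4.0% with none. The top figure needs a 15-point gap, and none of these gaps can be attributed to staff alone. The change is worth making because it costs little and acts before the data are collected.

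**What to change.** 1. In section 5.8, limit the statement to participants and staff who randomise, counsel or deliver treatment.
2. Hide the arm field in the REDCap follow-up forms. Section 5.5 confirms that access can be set by user.
3. Where existing staffing allows, have the 6- and 12-month contacts and sample requests made by someone who did not randomise or counsel that participant.
4. Fix one contact-and-sample sequence for everyone, including when the shortened survey and the CO device are posted.
5. Log attempts, and report attempts, reach and verification by arm, with self-reported beside verified abstinence.
6. State whether the odds-ratio sensitivity analyses apply within arm and whether they cover participants who were reached but not verified.

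The cost is form permissions, scheduling and a division of duties. Some unmasking by participants will remain. The documents give no staffing numbers, so it is an assumption that no new staff are needed. Sample size and power do not change.
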